This is a phase 4 open label feasibility study of extended release naltrexone (Vivitrol, Alkermes Pharmaceutical), case management and tele-addiction medicine for treatment of alcohol use disorders in the ED. The planned study period is 2 years. During this time we will conduct necessary department staff training and recruit 25 patients. Each patient will be followed for 12 months from index visit by our study staff, with case management provided by a full-time research case manager. Patients will be enrolled consecutively, 24 hours a day, 7 days a week. Recruitment will take place in the UCSF Emergency Department, Parnassus campus. Follow up visits may occur in the UCSF ED or an outpatient setting agreed upon by the patient and the research case manager. Patients who drop out of the study will be replaced with new patients; enrollment will end once 25 patients have been retained in the study or at the planned end date.

Initial Screening:

All adult patients presenting to the University of California San Francisco ED during the study period will be screened for frequent ED utilization (defined as 3 or more ED visits in the past 12 months including the index visit) by electronic medical record review conducted by the treating physician or member of the research team. UCSF, San Francisco General, and several other academic and community emergency departments in the San Francisco Bay Area share an electronic platform called the Emergency Department Information Exchange, or EDIE, that documents dates of ED visits and diagnoses. UC emergency providers can view visits at each of these sites, and ED visits to any hospital will be counted towards this 3-or-more threshold.

Determination of Eligibility:

An ED provider or staff (including physicians, advanced health practitioners, nurses, social workers, and case managers) may alert the PI or research study staff of potentially eligible patients based on the initial screen. The research team member will then determine eligibility as described below.

The PI [name], research fellow [name] or study staff (the research case manager) can all determine study eligibility. Initial eligibility will be determined based on chart review during the time of an ED visit. During study hours, the above mentioned faculty and staff will examine the

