The medical bracelet or wallet card will alert providers that opiate dosing adjustments may be necessary to adequately treat acute pain should the patient require treatment during the study period. It will provide information about the added precautions necessary should that patient require opioid pain management. Specifically, as the amount of opioid required to achieve adequate analgesia may be increased any resulting respiratory depression may be deeper and more prolonged. Therefore a fast acting agent is preferred and the amount of opioid analgesic should be titrated to the clinical effect in a setting equipped for cardiopulmonary resuscitation. The PI will be available by phone for emergency consultation at any time.

Visit 2-3 study procedures:

Patients will receive a monthly intramuscular injection of extended release naltrexone for up to 3 consecutive months during visits for which the research case manager will outreach to the participants in the community. Injections will be administered in an outpatient setting by an addiction community provider familiar with XR-Naltrexone, or in the UCSF ED depending on patient preference. A 20-dollar gift card incentive will be used to encourage follow-up at the time of each injection. We will follow participants for 12 months from the time of enrollment (an additional 9 months after the final dose of XR-NTX administered on behalf of the study). Specimens for alcohol biomarker testing will be collected at follow up visits.

At each of the monthly follow up visits we will collect data on a) feasibility measures and b) study outcomes. During the follow-up period, the research case manager will track all participants and we will continue to collect data on study outcomes using REDCap including ED and inpatient hospital use, substance use, readiness to change, and engagement in substance use recovery/rehabilitation via community treatment programs, as well as subsequent doses of XR-Naltrexone administered. This data will be collected by administering the same validated questionnaires used in the index visit (AUDIT, ASI, SIP-2R). The PI and research fellow will also query the EDIE system and UCSF EHR monthly in order to identify any emergency department visits that could be related to the study procedures.

Follow up procedures after visit 3:

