Patients who miss scheduled follow up injection visits will be contacted and asked to reschedule their injection visit as soon as possible. If they are able to reschedule within 2 weeks then no changes to study procedure are necessary. If they are able to reschedule within 2-4 weeks then they will be asked if they have used any opiates (including fentanyl) in the past 7 days. If they have not used opiates in the past 7 days then they will resume treatment, provided they are not endorsing any signs or symptoms of liver injury. If they endorse signs or symptoms of liver injury they will undergo screening as outlined above. If they endorse using opiates then they will not be allowed to resume treatment through the study. If a patient is unable to reschedule a missed injection appointment within one month they will not be allowed to continue in the study. If a patient is unable to resume treatment through the study then they will be provided with alternative follow up options (see transition to ongoing care).

Participant Payment:

A 20-dollar gift card incentive will be used to encourage attendance at the 6 monthly follow up visits required for XR-Naltrexone injections. Gift cards will be given at each of the six visits. The total value of gift cards available to each participant during the study period is \$120.00. Gift cards will be issued for locations that do not sell alcohol (e.g. Starbucks coffee).

Study Subjects:

The target population is patients with frequent ED visits for alcohol related complaints who may benefit from ED-initiated XR-NTX. The accessible population is all people in the San Francisco Bay Area presenting to the ED with an alcohol related complaint. The study sample will be adult

patients presenting to the UCSF ED with active hazardous or high risk alcohol use and ≥ 4 ED visits in the past 12 months for alcohol related complaints.

Inclusion Criteria:

- Age ≥ 21
- AUDIT score ≥ 8
- Frequent emergency department visits, defined as: At least 3 emergency department visits for in the past 12 months, including the index visit.

Exclusion Criteria:

- Opioid use: currently receiving opioid analgesics, self-report of opioid use in past 7 days, current physiologic opioid dependence, patients in acute opioid withdrawal, urine toxicology screen positive for opiates including fentanyl
- History of hypersensitivity to naltrexone, polylactide-co-glycolide (PLG), carboxymethylcellulose, or any other components of the diluent

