- LFTs $> 5x$ upper limit of normal or known cirrhosis
- Platelets less than 100,000 per cubic mm
- Acute condition at the time of enrollment that necessitates medical therapy with opioids
- Pregnant
- Incarcerated

Management of acute alcohol withdrawal:

XR-NTX is not a treatment for acute alcohol withdrawal. Acute alcohol withdrawal management will be left to the discretion of the treating physician.

Patients admitted to the hospital:

Hospital admission will not exclude an individual from study participation. The study medication will be delivered in the ED and the research case manager will follow the patient while he/she is an inpatient, and coordinate a follow-up plan with the admitting team at the time of hospital discharge.

III. Safety:

Adverse Events:

Serious adverse events have been reported to occur in $\sim 5\%$ of those treated with XR-NTX, which is similar to placebo [15]. Adverse events tend to be mild or moderate, with injection site pain, nausea, headache and fatigue being the most frequent.

The research case manager will collect information about adverse events at each monthly follow up visit and enter the data into RedCap data collection forms. Any unanticipated problems related to the study activities identified by the research team will be entered into the RedCap form as well. This data will be reviewed quarterly by the PI, who will determine if the event was expected, the severity of the event, and the likelihood that the event was related to the research study activities. Any serious adverse events will be reported to the PI immediately by the

research case manager, or any member of the research team who identifies a serious adverse event. The PI will report all serious adverse events resulting in death or possible life threatening events to the UCSF IRB immediately. All other adverse and unexpected events will be reported using the iRIS adverse event reporting forms within 5 business days of the PI becoming aware of the event.

Risks and risk minimization strategy:

Injection site pain, mild swelling, and possible ecchymosis are possible. The smallest acceptable needle size will be used and patients will be treated with non-narcotic oral analgesics as needed for bothersome injection site pain

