The risk of bias is substantial given that all enrollees are to be treated with XR-NRT and the study is not randomized or blinded and the population of interest is at high risk of being lost to follow up. We intend to conduct both an intention to treat analysis and a per protocol analysis, though our sample size may limit the utility of this approach. We will employ an independent data analyst to collect the ED visit counts and perform the final statistical analysis.

Statistical issues:

Statistical Test: Paired T Test

Hypothesis:

ED initiated Treatment of alcohol use disorders with multi-modal therapy reduces alcohol related ED visits in patients with frequent ED visits for alcohol related complaints

Sample Size:

We will enroll 25 patients. As a feasibility study our sample size was chosen as it represents a reasonable patient load for a single case manager. Because this population is difficult to retain in treatment, we anticipate the drop-out rate will be significant. Patients who drop out of the study (either withdraw or are lost to follow up) will be replaced with new enrollees until 25 patients have been recruited into the study. The goal of this practice is to maximize the benefit to the patient population, avoid wasting donated study medication, and to allow the research team to optimize recruitment and retention strategies.

Last year 42 patients presented to the UCSF Emergency Department at least 4 times for an alcohol related complaint. Of this group the mean number of visits was 8.49 with a SD of 8.58. The median number of visits was 6. The number of visits ranged from 4-47. After excluding 2 outliers (40 and 47 visits, each $> 3SD$ above the mean) the mean was 6.78 visits with a SD of 3.5 visits.

We estimate a standardized effect size of 0.584 would represent 2-5 emergency visits for alcohol related complaints. This equates to a 29-59% reduction in ED utilization, which is clinically relevant.

Data management plan:

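### Adverse-event questions are tied to attended monthly visits, so patients injected once who do not return have no solicited tolerability data, and no final summary covers all injected patients

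*Combined protocol and SAP*

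**What the plan says.** **Exposure.** Under Enrollment (section II), each patient who meets all criteria receives the study injection in the ED, before any follow-up has taken place.

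**Solicited collection.** Section III, Adverse Events: "The research case manager will collect information about adverse events at each monthly follow up visit". Under Risks and risk minimization strategy, liver symptoms are asked about at later injection visits.

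**Patients who do not return.** Handling of missed injection visits provides for contact to reschedule. Opioid use is asked about, and liver symptoms considered, if the new visit falls at 2-4 weeks. Then: "If a patient is unable to reschedule a missed injection appointment within one month they will not be allowed to continue in the study". The Sample Size text adds: "Patients who drop out of the study (either withdraw or are lost to follow up) will be replaced with new enrollees". The same text says "we anticipate the drop-out rate will be significant". Overview of Design states that "enrollment will end once 25 patients have been retained in the study or at the planned end date".

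**Other routes.** Under Visit 2-3 study procedures, the investigators "query the EDIE system and UCSF EHR monthly in order to identify any emergency department visits" that could be related to the study. Section III has any team member who identifies a serious event report it to the principal investigator, who reviews adverse-event data quarterly. A stakeholder committee also reviews adverse events quarterly. The Interim analysis after 10 patients is qualitative and covers reactions to the drug. Phone calls about once a month are described for the 9 months after the final injection visit.

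**Analysis.** Section IV lists feasibility, ED-visit, drinking, biomarker and cost outcomes, with intention-to-treat and per-protocol analyses. It has no adverse-event outcome, no safety analysis set and no denominator for adverse events.

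**The concern.** The injection comes first and the question about reactions comes later, at a visit that some patients will not attend. Those who had a bad reaction may be among the least likely to come back. Replacement then fills the study with patients who did come back, and they are the ones with completed forms.

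Section VI plans a proposal for a randomized trial after this study. How patients tolerate a first injection started in the ED is something readers of the pilot will look for. A rate drawn from returners alone, or one that treats silence as absence of events, could mislead them.

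**Working it through.** **Step 1. What is written for each kind of patient.**

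| Patient after the first injection | Contact written in the plan | Adverse-event question written |
|---|---|---|
| Attends monthly follow-up | Visit | Yes; liver symptoms also at injection visits |
| Misses, then reschedules within 2 weeks | Call, then visit | Yes, at the visit |
| Misses, then reschedules at 2-4 weeks | Call, then visit | Yes, at the visit; opioid use and liver symptoms checked before resuming |
| Misses, does not reschedule within one month | Call to reschedule | None; cannot continue, and is replaced if counted as a drop-out |
| Completes the third injection visit | Calls about monthly for 9 months | Health changes after the treatment period |

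The fourth row is the gap. The record query needs an ED visit. The events that section III calls most frequent (pain at the injection site, headache, fatigue, nausea) would seldom lead to one.

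**Step 2. Is there a planned figure to reproduce?** Not for safety. The only design figure is in Sample Size: "We estimate a standardized effect size of 0.584 would represent 2-5 emergency visits for alcohol related complaints". A paired t test with 25 patients, two-sided 5% and 80% power (both assumed, as neither is stated) detects 0.584. On the visit scale, 0.584 × 3.5 = 2.04 and 0.584 × 8.58 = 5.01. The figure reproduces and has no bearing on this point.

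**Step 3. How many patients could be affected?** The non-return proportion d is an assumption, taken as 20%, 30% and 50%. If 25 must be retained, the number injected is 25/(1 − d), rounded up:
- d = 20%: 25/0.8 = 31.25, so 32 injected and 7 without solicited data
- d = 30%: 25/0.7 = 35.7, so 36 injected and 11 without
- d = 50%: 25/0.5 = 50 injected and 25 without

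**Step 4. Which way would a reported rate move?** Let pr be the event risk in returners and pn the risk in non-returners. The true rate is (1 − d)·pr + d·pn. The rate in returners is pr. The rate over all injected, with non-returners counted as event-free, is (1 − d)·pr. With pr = 30% (assumed):

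| d | True rate if pn = 30% | if pn = 45% | if pn = 60% | Returners only | All injected, non-returners event-free |
|---|---|---|---|---|---|
| 20% | 30% | 33% | 36% | 30% | 24% |
| 30% | 30% | 34.5% | 39% | 30% | 21% |
| 50% | 30% | 37.5% | 45% | 30% | 15% |

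The returner-only rate is unbiased when pn = pr and too low when pn > pr. It is too high when pn < pr: with pn = 15% and d = 30%, the true rate is 0.7 × 30% + 0.3 × 15% = 25.5%, against 30% seen. The event-free convention is too low even when pn = pr, by the factor 1 − d (0.80, 0.70, 0.50).

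**Step 5. What honest bounds would look like.** With non-contacts counted as all event-free and then all with an event, the bounds are (1 − d)·pr and (1 − d)·pr + d. For pr = 30% they are 24% to 44%, 21% to 51% and 15% to 65%. Their width is d, the proportion not contacted, so extra phone contact narrows them directly.

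**The case against.** The plan is not silent on safety. It has an interim look at adverse events, quarterly review by the principal investigator and by a committee, reporting of serious events and a monthly record query. Patients without a phone may be issued one, patients can call the case manager, and those who miss visits are contacted. Overview of Design promises 12 months of follow-up for each patient, and Visit 2-3 study procedures has the case manager track all participants. This is a phase 4 feasibility study of an approved drug, and precision will be poor: with no events in 25 patients, the one-sided 95% upper limit is 1 − 0.05^(1/25) = 11.3%. An extra call will not reach everyone who is lost, and patients who withdraw may refuse contact.

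Much of this stands, and it rules out three stronger readings that a reader might infer.
- **That no safety result is planned.** The interim look and the reviews are planned. What is absent is a final summary over all injected patients.
- **That non-returners are wholly unobserved.** Record-based and unsolicited routes exist. Whether they continue after a patient is barred is unclear, because the 12-month promise and the one-month rule are not reconciled.
- **That the drug will look better tolerated than it is.** No section counts non-returners as event-free, and Sample Size attributes drop-out to a population that is hard to retain, not to reactions. Large bias needs strong assumptions. Suppose the true rate is 30%, a reaction doubles the chance of non-return, and 50% do not return. Returners would then show about 14%, but 2 × 0.5/1.3 = 77% of patients with a reaction would have to stay away.

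None of this supplies a tolerability question for the patient who is injected once and does not return. The reviews can weigh only what has been recorded.

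**Conclusion.** The point holds as a gap in collection and reporting. As written, a patient injected once who does not return has no solicited adverse-event data, and no final table covers everyone exposed. First-injection tolerability may be understated if non-return is linked to reactions or if silence is counted as no event; neither condition is established by the documents. The size cannot be derived from them. The 7 to 25 patients and the rates in the working rest on assumed non-return of 20% to 50%, an assumed 30% event rate and, for the counts, the reading that 25 must be retained. The missing safety outcome alone would be a matter of detail. With the collection gap it is worth correcting, because mild events not asked about at the time are hard to recover.

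**What to change.** 1. **Collection** (section III, Adverse Events, and section II, Handling of missed injection visits). For every injected patient who does not attend, complete the existing REDCap adverse-event form by phone, at the missed-visit contact or about a month after each injection. Include patients who stop injections or are replaced, unless they withdraw consent to contact.
2. **Reporting** (section IV). Give the number and percent with any adverse event, any serious event and an injection-site reaction, with exact 95% intervals, among all patients with at least one injection, including those replaced. Also give the number with no adverse-event contact after their last dose, the rate among those contacted, and the bounds in step 5 of the working. Include events found by the monthly record query.
3. **Reconciliation.** Reconcile the 12-month follow-up of each patient (Overview of Design; Visit 2-3 study procedures) with the statement that some patients may not continue (Handling of missed injection visits), so that it is clear that follow-up and record queries go on after injections stop. Visit 2-3 study procedures, with up to three injections, also disagrees with the six injection visits under Participant Payment. That needs reconciling too, because it sets how often the form is due.

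None of this alters a dose or a treatment rule. The cost is protocol wording, a few extra phone forms with existing staff and one extra table. Some patients will still be unreachable, and the reported rate may be higher with a wider range.

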XR-Naltrexone carries a risk of drug induced hepatitis. Patients will be screened with liver function tests, questioned about medical history of liver disease, and have their medical record reviewed by the emergency medicine provider to screen for history of liver disease. Patients with cirrhosis or aminotransferase levels (AST, ALT) greater than 5x the upper limit of normal will be excluded. Participants will be questioned at subsequent XR- NTX administration visits about signs and symptoms of liver injury (upper abdominal pain, abdominal bloating, vomiting, yellowing of the skin or eyes, severe fatigue/weakness, joint and muscle pain). Answers to these questions will be reviewed weekly by the PI and clinical research fellow. If the PI and/or fellow believe the participant is exhibiting evidence of liver injury, they will arrange a follow up visit at the UCSF ED within one week. At that visit if the PI or fellow feels there is sufficient clinical concern for liver injury, then laboratory testing of liver function will be conducted during the visit. Any liver function testing that occurs as a result of the PI/fellow's concern for liver injury will be considered research specific testing and outside routine clinical care. The results of any laboratory tests done to evaluate for XR-NTX induced organ injury will be followed up by the PI or clinical research fellow. Subsequent injections of XR-NTX will not be given until the PI/clinical fellow have the results and confirmed that it is safe for the patient to continue treatment. If the liver aminotransferase concentrations rise to >5 times the upper limit of normal the study medication will be discontinued and the aminotransferases will be repeated in one week. If on repeat testing the aminotransferase elevation is again above 5 times the upper limit of normal the patient will be referred for Hepatology evaluation.

XR-Naltrexone is a deep intramuscular injection and additionally carries some risk of lowering platelet counts, typically by less than 20,000 per cubic mm. Patients with platelet counts below 100,000 per cubic mm. will be excluded in order to minimize the risk of bleeding.

As with any medication, XR-Naltrexone intramuscular injection carries a risk of allergic reactions including anaphylaxis. Patients with known allergy to naltrexone or any of the inactive ingredients of the injection will be excluded.

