Data collected for this study includes details about alcohol and recreational drug use as well as information about employment and housing status. These topics may be sensitive to discuss, but are part of routine medical interviewing. Information collected by the research team will be taken place in a private room and data stored securely (see data management plan).

No EDs in San Francisco administer Naltrexone, so there is no concern that a patient will receive extra doses during ED visits at locations other than UCSF. There are community sites, such as the San Francisco sobering center, SF street medicine and Health Right 360, where XR-Naltrexone is available and is administered to patients. These community sites are key stakeholders in the treatment of patients with AUD. One of the aims of this study is to establish a robust referral network for ongoing treatment of AUD once patients are discharged from the hospital/ED by mobilizing key stakeholders. We will coordinate with leadership and staff of community organizations that treat AUD throughout the study timeframe by forming a stakeholder committee that includes representatives from SF Street medicine, Health Right 360, and UCSF providers about both facilitators of and barriers to continuity of care after the initial ED visit and throughout the study. The committee will also serve as a venue for stakeholders to express any safety concerns, and will review any adverse events. The committee will meet quarterly and will record meeting proceedings and create a meeting summary.

Risk/Benefit balance:

XR-Naltrexone is FDA approved for the treatment of alcohol use disorders and has an excellent established safety profile. The serious adverse drug event rates are low and the drug is generally well tolerated. Based on available evidence, it is the most effective pharmacotherapy for alcohol use disorders. The benefits to participants of receiving a safe, established, effective treatment for their alcohol use disorder include reduction in total alcohol consumed, reduction in heavy drinking days, and increased success with achieving sobriety if desired. Based on current research literature, reduced days of heavy drinking and total alcohol use can be reasonably expected to lower the risk of alcohol related disease and alcohol related trauma. These are associated with significant cost, both personal and financial, to both patients and society.

IV. Analysis, Measurements, and Outcomes:

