The research case manager will use a tablet device to enter data into data entry forms in REDCap. The research case manager will also maintain a back-end Microsoft Access database. The REDCap data collection system is secure will be accessible only to members of the study team. The back-end Access database will be maintained on MyResearch in a folder accessible only to members of the study team. REDCap and MyResearch are on secure servers and are backed up regularly. When data are exported to STATA for statistical analysis, patients will be identified by a SubjectID that has no meaning external to the database. No dates will be exported.

Interim analysis:

We will conduct a qualitative analysis after 10 enrolled patients to assess **enrollment** (enrollment rate, number of patients who do not meet inclusion criteria, unanticipated barriers to enrollment), **retention** (study retention rate, unanticipated barriers to retention, proportion of follow up visits in ED vs at patient's home or in the community), and adverse events that might be related to the study at that time including adverse reactions to the study drug. We do not anticipate adverse events occurring as a result of this study, because of the safety profile of the study drug and the fact that we are offering new, additional services to assist patients with treatment for alcohol use disorder, which are low-risk activities.

V. Personnel, resources, and partnerships:

UCSF will provide a full-time research fellow (board eligible Emergency Medicine physician), as well as other board certified Emergency Medicine physicians, RNs, and pharmacists, to assist with screening and enrolling patients, administering and storing medication, coordinate follow up, and perform data analysis.

Procedures other than injection of the study drug carried out as part of routine care during the index visit and with community healthcare providers services occurring after the index visit will be charged to the participant's insurance.

The cost of procedures done for research purposes only including urine drug screening, urine fentanyl screening, and repeat liver function testing for participants with suspected liver injury will be paid for by the study.

The study will pay for all doses of the study drug administered as part of this study (up to 3 per participant).

VI. Brief Proposed Timeline:

- May-July 2019- Submit for IRB approval and grant proposals

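### Quarterly PI review of non-serious adverse events is slower than the three-dose course, and no liver-symptom check is specified after the last dose

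*Combined protocol and SAP*

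**What the plan says.** **Recording and review (section III, Adverse Events).** "The research case manager will collect information about adverse events at each monthly follow up visit". Unanticipated problems go into the same REDCap form. Then: "This data will be reviewed quarterly by the PI, who will determine if the event was expected, the severity of the event", along with its likely relation to the study.

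**Faster routes.**
- Serious events reach the PI at once from the "research case manager, or any member of the research team who identifies a serious adverse event" (Adverse Events).
- Answers to the liver-symptom questions are looked at weekly by the PI and the clinical research fellow (Risks and risk minimization strategy).
- The PI and fellow search EDIE and the UCSF record monthly for ED visits that might be study-related (Visit 2-3 study procedures).

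**IRB reporting.** Deaths and possibly life-threatening serious events go to the IRB immediately. Everything else "will be reported using the iRIS adverse event reporting forms within 5 business days of the PI becoming aware of the event".

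**Other looks at adverse events.** On the stakeholder committee: "The committee will also serve as a venue for stakeholders to express any safety concerns, and will review any adverse events". Its timing: "The committee will meet quarterly and will record meeting proceedings and create a meeting summary". The single interim look, after 10 enrolled patients, covers "adverse events that might be related to the study at that time including adverse reactions to the study drug".

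**Liver symptoms.** "Participants will be questioned at subsequent XR- NTX administration visits about signs and symptoms of liver injury". Patients resuming 2-4 weeks late must also be free of liver symptoms (Handling of missed injection visits). After the third injection visit, roughly monthly calls collect outcomes and ask in general terms about treatment and health (Follow up procedures after visit 3).

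**The concern.** Doses are monthly, up to three, so the whole course fits inside one review quarter. A report made at visit 2 can easily wait past dose 3 before a physician on the study team judges its severity or relatedness. The only written hold on an injection is for pending liver tests. The protocol itself names drug risks that could first appear as non-serious, non-liver complaints: injection-site swelling and ecchymosis, lowered platelets and allergic reactions. Bruising or a mild allergic reaction bears on whether to give another deep intramuscular injection. The case manager who records events is the one team member not described as a practicing emergency physician (Consent), and patients may change injection site at any time, so whoever gives dose 3 may not have seen the visit-2 report.

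The IRB clock starts at PI awareness. For this group of events the quarterly review is the only specified adverse-event route to the PI.

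The second gap is that the protocol names drug-induced hepatitis as a risk but ties its symptom list to giving further drug. Someone who simply stops after dose 1 is never asked it, and the Sample Size section expects significant drop-out.

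**Working it through.** The plan gives no figure on this point, so there is none to reproduce.

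**Inputs.**
- Review interval: quarterly, taken as 91 days (Adverse Events).
- Visit 2 to dose 3: one month, taken as 28 to 30.4 days (Visit 2-3 study procedures).
- Late visits: up to 2 weeks late with no change; 2-4 weeks late with extra questions (Handling of missed injection visits).
- IRB deadline: 5 business days, taken as 7 calendar days.
- Assumption: review dates fall uniformly relative to a participant's visit 2. The documents give no dates.

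**Course length.** First to third dose: 2 × 28 = 56 days (8.0 weeks) to 2 × 30.4 = 60.8 days (8.7 weeks), against 91 days between reviews. Participant Payment speaks of six injection visits, whereas the treatment sections allow up to three doses. Three is used here, and the visit-2 to dose-3 interval is the same either way.

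**Share of visit-2 reports with no PI review before dose 3** = 1 − (days from visit 2 to dose 3)/91.

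| Dose 3 | Calculation | Share |
|---|---|---|
| On schedule | 1 − 28/91; 1 − 30.4/91 | 69%; 67% |
| 2 weeks late | 1 − 42/91; 1 − 44.4/91 | 54%; 51% |
| 4 weeks late | 1 − 56/91; 1 − 58.4/91 | 38%; 36% |

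With weekly review the on-schedule share is 0, since 28 days exceeds 7.

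**If the quarterly committee counted as a second look (on schedule).** The share unseen by either is:
- same dates as the PI review: 67-69%;
- independent dates: 0.666² = 0.44 to 0.692² = 0.48;
- evenly staggered, so one look every 45.5 days: 1 − 30.4/45.5 = 0.33 to 1 − 28/45.5 = 0.38.

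**Interim look.** With even accrual of 25 patients over 16 months (assumption, from the timeline's March 2020 to June 2021), patient 10 enters at 10/25 × 16 = 6.4 months. About 25/16 = 1.6 patients would then be between visit 2 and dose 3.

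**Time from record to IRB report**, if the PI learns of the event only at review. The 7 days are a ceiling, so each mean is a range.
- Quarterly: maximum 91 + 7 = 98 days; mean 91/2 = 45.5 to 45.5 + 7 = 52.5 days.
- Weekly: maximum 7 + 7 = 14 days; mean 7/2 = 3.5 to 3.5 + 7 = 10.5 days.

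**Scheduled liver-list checks.**

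| Patient | At visit 2 | At visit 3 | After last dose |
|---|---|---|---|
| Completes three doses | yes | yes | none; general health question on calls |
| Stops after dose 2 | yes | – | none |
| Stops after dose 1 | – | – | none |

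The tracking data listed under Visit 2-3 study procedures (ED and hospital use, substance use, readiness to change, treatment engagement, later doses) contain no liver-symptom item.

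**The case against.** The strongest reply is that this is a deliberate and proportionate tiering. The study is a 25-patient, open-label feasibility study of an approved drug. Serious events go up immediately, liver answers weekly, ED visits monthly, and only the lowest tier waits for a quarter. No rule in the documents is broken. That stands, and it is why the point is minor.

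The remaining group is also narrower than it first looks. The liver list includes vomiting, severe fatigue or weakness, abdominal pain and joint or muscle pain, so some common complaints already get weekly review. Injection-site pain has its own management plan. Adverse events are asked about again at the dose 3 visit, and the person injecting may use judgement. All of this stands.

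Other routes to the PI exist: the bracelet or wallet card with contact details, the PI's emergency phone line (described for opioid analgesia), and the drug-ordering steps. Any of them could shorten the 98 days in practice. None is a specified adverse-event review before dose 3, and neither the committee nor the one-off interim look is described as one.

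Three stronger readings are tempting but not supported:
- *Most adverse events go unreviewed before dose 3.* The share applies only to the residual group, and only under the timing assumption.
- *A given number of patients will be dosed before review.* The documents give no event rate and expect drop-out, so no count can be derived.
- *There is no safety follow-up after the last dose.* Completers get about nine months of calls that ask about their health, ED visits are queried monthly, and serious events are reported immediately. What is missing is a named liver check.

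**Conclusion.** Both parts hold as a minor patient-safety point. Neither affects the feasibility outcomes or the paired t test.

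For non-serious, non-liver events that do not lead to an ED visit, roughly two thirds of visit-2 reports would have no scheduled PI review before an on-schedule dose 3, falling to a little over one third if dose 3 is 4 weeks late. This rests on review dates being random relative to visits. The IRB delay rests on the PI not hearing of the event another way.

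The liver part needs no timing assumption. It matters most for patients who stop early: after dose 1 they are never asked the list, and after dose 2 they are not asked it again. For completers the gap is small.

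**What to change.** **Adverse Events (section III).** Have the PI or clinical research fellow review the adverse-event forms weekly, together with the liver-symptom answers, and in any case before that participant's next injection. Keep the quarterly review as a summary. The link to the next injection matters, because a faster review alone would still leave dose 3 independent of it.

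**Risks and risk minimization strategy (section III).** Add one liver-symptom and adverse-event check about one month after the last injection. Use the first post-treatment call for completers and the missed-visit contact for patients who stop after dose 1 or 2. Send the answers to the same weekly review.

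**Cost.** Protocol wording, existing forms, contacts already planned and a few minutes of PI or fellow time per week. Two limits remain: patients who cannot be reached are still missed, and an event first reported at the dose 2 visit still cannot inform dose 2.
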